ACURATE Prime XL Nested Registry Statistical Hypothesis	Mean aortic valve pressure gradient at 30 days post implant procedure is less than a performance goal (PG): $H_0$ : Gradient 30D $\geq$ PG $H_1$ : Gradient 30D $<$ PG where Gradient 30D is the 30-day mean aortic valve pressure gradient for the ACURATE Prime XL valve and PG is 15 mmHg.
Statistical Test Method for the ACURATE Prime XL Nested Registry	A one-sample t -test will be used to test the one-sided hypothesis at a significance level of 2.5%.
Sample Size Parameters for the ACURATE	
 
Expected 30-day mean pressure gradient from ACURATE Prime XL = 10 mmHgh
 
Expected standard deviation = 7 mmHg
 

Prime XL Nested Registry	
 
PG = 15 mmHg
 
Test significance level (α) = 0.025 (1-sided)
 
Power > 90%
 
Evaluable number of subjects = Minimum of 40 subjects
 
Expected rate of attrition = 20% (8 subjects)
 
Planned enrollment of 50 subjects
 
The analysis population for the hypothesis testing will be the subject population implanted with the ACURATE Prime XL valve.
 
h: Based on Boston Scientific data on file and published data for large-annulus CoreValve devices: Tang GHL, et al. Am J Cardiol 2019;124:1091-8 Kalogeras K, et al. Catheter Cardiovasc Interv 2019;93:685-91 Ussia GP, et al. EuroIntervention 2015;10:e1-e8
 

Success Criteria for the ACURATE Prime XL Nested Registry	If the P value from the one-sample t -test is $< 0.025$ , the ACURATE Prime XL valve will be concluded to have a 30-day mean aortic valve pressure gradient $< 15$ mmHg. This corresponds to the one-sided upper 2.5% confidence bound of the observed 30-day mean aortic valve pressure gradient being $< 15$ mmHg.
Statistics Summary	Data will be summarized separately for each cohort. In addition to the hypothesis tests listed above, descriptive statistics will be used. Full methods will be described in the statistical analysis plan.

## 2 INTRODUCTION

The study is designed to assess the safety and effectiveness of the ACURATE Transfemoral Aortic Valve System for transcatheter aortic valve replacement (TAVR) in subjects with severe native aortic stenosis who are indicated for TAVR. This analysis plan specifies the detailed statistical methods and definitions used for the endpoint analyses and statistical data reporting.

#### **3 ENDPOINT ANALYSIS**

The Main Randomized Cohort data from the ACURATE IDE trial will be used for the primary endpoint analysis (including 4D CT subjects). Data will also be summarized separately for the randomized subjects in the 4D CT Imaging Substudy.

Data will be summarized separately for subjects in the ACURATE IDE roll-in cohort, Extended Durability Cohort, and Continued Access Study cohorts. Descriptive statistics will be used to summarize the data in these cohorts and no statistical inference will be made. Data will be summarized separately for the specific statistical hypothesis associated with the ACURATE *Prime*TM XL Nested Registry. Descriptive statistics also will be used to summarize data from subjects in the single-arm ACURATE *Prime* XL cohort.

### 3.1 Primary Endpoint for the Main Randomized Cohort

The primary endpoint for the Main Randomized Cohort is the composite of all-cause mortality, all stroke, and rehospitalization† at 1 year. The events in this endpoint will be adjudicated by an independent CEC.

†Hospitalization for valve-related symptoms or worsening congestive heart failure (NYHA class III or IV); per VARC-2 definition.

## 3.1.1 Hypotheses

The statistical hypothesis is that the primary endpoint (composite of all-cause mortality, all stroke, and rehospitalization at 1 year) rate for the ACURATE (test) group is non-inferior to that for the Control group.

The null and alternative hypotheses for the primary endpoint are as follows:

H0:  $P_{E\_ACURATE}$  minus  $P_{E\_Control} \ge \Delta$  (Inferior)

H1:  $P_{E_ACURATE}$  minus  $P_{E_Control} < \Delta$  (Non-inferior)

where  $P_{E\_ACURATE}$  and  $P_{E\_Control}$  correspond to the primary endpoint rates for the ACURATE and the Control group, respectively, and  $\Delta$  is the non-inferiority margin.

The primary analysis set for the primary endpoint is the ITT analysis set. This endpoint will also be analyzed for the implanted analysis set.

A Bayesian analysis will be performed to estimate the treatment difference between ACURATE and Control through posterior probability.

## 3.1.2 Sample Size

Although the primary endpoint analysis is performed using the Bayesian method, the sample size calculation for the Main Randomized Cohort is based on a standard non-inferiority two-sample test approach with one formal interim analysis planned. The sample size calculation for the primary endpoint is based on the following assumptions.

- Expected rate for both arms = 22.3% (based on a weighted average of TAVR data
- Non-inferiority margin ( $\Delta$ ) = 8.0% (36% relative to expected rate)
- Test significance level ( $\alpha$ ) = 0.025 (1-sided)
- Test (ACURATE): Control ratio = 1:1
- Power  $(1 \text{ minus } \beta) > 90\%$
- Expected rate of attrition = 5%
- Total sample size = 1500 (750 per group)
- Number of evaluable subjects per group = 712
- Analyses: One administrative, one formal interim, one final

The Pocock-type method is used during sample size calculations when 70% subjects reached 1-year follow-up at the formal interim analysis. The statistical software EAST® 6.5 is used for the sample size calculations.

The estimated proportions of subjects in the Main Randomized Cohort by operative risk level are 10% extreme risk, 25% high risk, 30% intermediate risk, and 35% low risk.

The formal interim analysis will be carried out after enrollment in the Main Randomized Cohort is completed. This formal interim analysis will be conducted on the full N=1500 subjects of the Main Randomized Cohort after first 1050 subjects in the Main Randomized Cohort have completed 1-year follow-up or at least 80% low risk subjects in the Main Randomized Cohort have completed 6-month follow-up, whichever comes later. The piecewise exponential models will be based on outcomes among these subjects who have completed 30-day, 6-month, or 1-year follow-ups. The results from the models will be used to estimate the 1-year results by treatment group through Bayesian posterior probabilities for the non-inferiority test. The final analysis for the primary endpoint will be performed on all subjects with completed 1-year data if non-inferiority cannot be claimed at the formal interim analysis.

#### 3.1.3 Success Criteria

The Bayesian method is used to test the non-inferiority hypothesis of the primary endpoint. To establish that the ACURATE device is non-inferior to the Control, the results will need to meet the following equation:

 $Pr(H_1 | Data) > \xi$ 

where

- Pr(H1 | Data) is the posterior probability of H1 given the observed data at either the interim or the final analysis;
- H1 is the alternative hypothesis for non-inferiority: PE ACURATE minus PE Control  $< \Delta$ ;
- ξ is a prespecified threshold, which is empirically chosen through extensive simulations using the Bayesian approach for the noninferiority tests.

If non-inferiority has been declared at the formal interim analysis, the non-inferiority test will not be performed at the final analysis. If non-inferiority cannot be declared at this interim analysis, the non-inferiority test will be performed at the final analysis for all subjects using the Bayesian method with the same pre-specified threshold. The study will not stop for futility at the interim analysis.

## 3.1.4 Bayesian Statistical Methods

## 3.1.4.1 Piecewise exponential survival model

The primary endpoint event rates for the hypothesis test specified in Section 3.1.1 will be estimated through posterior probabilities of the hazards from the piecewise exponential survival models. The piecewise exponential models will be constructed by subject operative risk (extreme/high, intermediate, and low). To simplify the notations, the formulas in the Section 3.1.4 represent the general notations within each risk stratum and the same notations can be applied to the data for each risk stratum.

Within each risk stratum, the time partition for the piecewise exponential models between 0-365 days is defined as:

 $0 = t_0 < t_1 < t_2 < t_3 = 365$ , where  $t_1 = 30$  and  $t_2 = 180$ The hazard rates will be estimated for the three intervals:  $\tau_1: [t_0, t_1], \tau_2: (t_1, t_2]$ , and  $\tau_3: (t_2, t_3]$ . The hazard within each time interval is considered as constant by treatment group.

Within each time intervals, the piecewise exponential models will be generated by treatment group (test and control). Let  $\lambda_{j,k}$  denote the hazard rate for subjects in the jth treatment group and the kth time interval, j=1, 2 and k=1, 2, 3, where the indices are defined as the following:

j is for treatment groups (1: test arm, 2: control arm),

k is for the time intervals (1: [0,30], 2: (30, 180], 3: (180, 365]) There will be total six estimated the hazard rates within each risk stratum.

Based on the estimated hazard rates  $\lambda_{j,k}$  from the models, the estimated probability of a subject who is in the jth treatment group developing an event at time  $\tilde{t}$  is defined as:

$$P_{j}(\tilde{t};\lambda_{j,k}) = \begin{cases} 1 - e^{-(\lambda_{j,1}*(\tilde{t}-t_{0}))}, & t_{0} \leq \tilde{t} \leq t_{1} \\ 1 - e^{-(\lambda_{j,1}*(t_{1}-t_{0})+\lambda_{j,2}*(\tilde{t}-t_{1}))}, & t_{1} < \tilde{t} \leq t_{2} \\ 1 - e^{-(\lambda_{j,1}*(t_{1}-t_{0})+\lambda_{j,2}*(t_{2}-t_{1})+\lambda_{j,3}*(\tilde{t}-t_{2}))}, t_{2} < \tilde{t} \leq t_{3} \end{cases}$$

Where  $\lambda_{j,k} = (\lambda_{j,1}, \lambda_{j,2}, \lambda_{j,3}).$ 

#### 3.1.4.2 Prior distribution

For the piecewise exponential models, the Gamma distribution is used as the prior distribution  $\lambda_{j,k} \sim Gamma(a, b)$  for the hazard parameters. The Gamma distribution Gamma(a, b) has the following PDF:

$$f_{a,b}(\lambda_{j,k}) = b^a \lambda_{j,k}^{a-1} e^{-b\lambda_{j,k}} / \Gamma(a), a, b > 0, \lambda_{j,k} > 0$$

where  $\Gamma(a)$  is a Gamma function, a is the shape parameter and b is the inverse-scale parameter.

The Gamma distribution for the prior uses the shape parameter a = 0.0001 and the inverse-scale b = 0.0001. The mean of the prior distribution is equal to 1 with a variance of 10000. The independent Gamma prior will be used for all parameters  $\lambda_{j,k}$ . This prior is proper and reasonably noninformative.

#### 3.1.4.3 Posterior probability

Let  $\lambda_j$  denotes the vector of parameters  $(\lambda_{j,1}, \lambda_{j,2}, \lambda_{j,3})$  for the hazard rates from the model of jth treatment group.  $L(D_j|\lambda_j)$  is the likelihood function defined as:

$$L(D_j|\lambda_j) = \prod_{k=1}^{3} (\lambda_{j,k})^{d_k} \times e^{-\lambda_{j,k} * T_k}$$
$$d_k = \sum_{m=1}^{n} I_{\tau_k}(\tilde{t}_m)$$

$$T_{k} = \sum_{m=1}^{n} J_{\tau_{k}}(\tilde{t}_{m})$$

$$I_{\tau_{k}}(\tilde{t}_{m}) = \begin{cases} 1, if \text{ event occurred at } \tilde{t}_{m} \in \tau_{k} \\ 0, if \text{ no event occurred up to } \tilde{t}_{m} \in \tau_{k} \end{cases}$$

$$J_{\tau_{k}}(\tilde{t}_{m}) = \begin{cases} \tilde{t}_{m} - t_{k-1}, if \ t_{k-1} \leq \tilde{t}_{m} < t_{k} \\ t_{k} - t_{k-1}, if \ \tilde{t}_{m} \geq t_{k} \\ 0, \quad if \ \tilde{t}_{m} < t_{k-1} \end{cases}$$

where  $0 \le \tilde{t}_m \le 365$ , m=1, ..., n.  $\tilde{t}_m$  is the number of days that the mth subject has been in the study. The *n* is the number of subjects in  $D_j$ . The  $D_j$  is the observed data for the jth treatment arm to fit the model.  $\tau_1: [t_0, t_1], \tau_2: (t_1, t_2]$ , and  $\tau_3: (t_2, t_3]$ , where  $t_0 = 0$ ,  $t_1 = 30$ ,  $t_2 = 180$ , and  $t_3 = 365$ .

The posterior distribution is proportional to a joined distribution of the prior and likelihood function that can be constructed as following:

$$\Pr(\lambda_j | D_j) \propto f_{a,b}(\lambda_j) * L(D_j | \lambda_j) \propto \lambda_j^{(a+d_k)-1} e^{-(b+T_k)\lambda_j}$$

 $Pr(\lambda_j | D_j)$  follows a gamma distribution that the shape parameter equals to  $(a + d_k)$  and the inverse-scale parameter equals to  $(b + T_k)$ , where k=1, 2, 3 and a = 0.0001, b = 0.0001.

The posterior distribution for each lambda is in the closed form of a Gamma distribution. Deriving the full conditional posterior distributions of the primary endpoint can be mathematically challenging. As stated in User's Guide Introduction to Bayesian Analysis Procedure: "When models become too difficult to analyze analytically, you have to use simulation algorithms, such as the Markov chain Monte Carlo (MCMC) method to obtain posterior estimates". Bayesian piecewise exponential model method will use the Markov chain Monte Carlo (MCMC) method to simulate posterior distributions of all lambdas. The posterior distributions of the primary endpoint then can be constructed based on the posterior distributions of the lambdas and the prespecified piecewise exponential models. The statistical inference for the primary endpoint will be based on the simulated posterior distributions of the lambdas and the constructed posterior distributions of the primary endpoint. The sampling algorithm for the posterior distributions implemented in SAS could be found in the SAS Proc MCMC procedure. The posterior distribution of the lambda for each interval will be independently constructed using the Metropolis-Hastings algorithm based on the likelihood function and a time-to-event data for a specific time interval.

Reference:

SAS/STAT®14.1 User's Guide Introduction to Bayesian Analysis Procedure, SAS Institute Inc.

SAS Manual, https://support.sas.com/documentation/onlinedoc/stat/131/mcmc.pdf

#### 3.1.5 Interim Analysis

#### 3.1.5.1 Completed visits at 30-day, 6-month, and 1-year

The interim analysis for the primary endpoint will be conducted after 1050 subjects in the Main Randomized Cohort have completed a 1-year follow-up, or at least 80% low risk subjects in the Main Randomized Cohort have completed a 6-month follow-up, whichever comes later. A subject is considered as completion of 1-year follow-up if the subject meets the following by the pre-specified cutoff date (defined in 3.1.5.2):

- 1) has completed 1-year follow-up visit, or
- 2) has not completed 1-year follow-up visit and is reported in the 1-year visit form as 'not done' or in the End-of-Study form (as died, withdrew, or lost to 1-year follow-up) and has reached 365 days post index procedure (or randomization if no procedure), or
- 3) has not completed 1-year follow-up visit and is not reported as 'not done' or not in the End-of-Study (as died, withdrew, or lost to 1-year follow-up) and has reached 395 days post index procedure (or randomization if no procedure).

Similarly, a subject is considered as completed 30-day and 6-month follow-up visits as the following:

For 30-day visit by the pre-specified cutoff date (defined in 3.1.5.2):

- 1) has completed 30-day follow-up visit, or
- 2) has not completed 30-day follow-up visit and is reported in the 30-day visit form as 'not done' or in the End-of-Study form (as died, withdrew, or lost to 30-day follow-up) and has reached 30 days post index procedure (or randomization if no procedure), or
- 3) has not completed 30-day follow-up visit and is not reported as 'not done' or not in the End-of-Study (as died, withdrew, or lost to 30-day follow-up) and has reached 37 days post index procedure (or randomization if no procedure).

For 6-month visit by the pre-specified cutoff date (defined in 3.1.5.2):

- 1) has completed 6-month follow-up visit, or
- has not completed 6-month follow-up visit and is reported in the 6-month visit form as 'not done' or in the End-of-Study form (as died, withdrew, or lost to 6month follow-up) and has reached 180 days post index procedure (or randomization if no procedure), or
- 3) has not completed 6-month follow-up visit and is not reported as 'not done' or not in the End-of-Study (as died, withdrew, or lost to 6-month follow-up) and has reached 210 days post index procedure (or randomization if no procedure).

#### 3.1.5.2 Formal interim analysis cutoff date and analysis cohorts

A cutoff date for the interim analysis is the date when the first 1050 subjects in the Main Randomized Cohort have completed a 1-year follow-up or at least 80% low risk subjects in the Main Randomized Cohort have completed a 6-month follow-up, whichever comes later. All subjects who have completed 30-day, 6-month, or 1-year (defined in Section 3.1.5.1) prior to or on the cutoff date should be included in the 30-day, 6-month, or 1year analysis cohort, respectively. The three analysis cohorts will be used for the piecewise exponential models for different time intervals, defined as the following:

- 30-day analysis cohort will be used for piecewise exponential models between 0-30 days.
- 6-month analysis cohort will be used for piecewise exponential models between 31-180 days.
- 1-year analysis cohort will be used for piecewise exponential models between 181-365 days.

Note: the analysis cohorts (30-day, 6-month, 1-year) are for ITT analysis. The analysis cohorts for the Implanted analysis will the subset of the ITT set for subjects who meet the Implanted definition.

#### 3.1.5.3 Models for estimating parameters

The piecewise exponential survival model will be constructed separately for each risk stratum (extreme/high, intermediate, and low), each treatment group (test and control), and each time interval (30-day, 6-month, and 1-year) on subjects who have completed respective visits. There will be total eighteen models (nine models within each treatment group). Each model will estimate one parameter of the lambdas and simulate the corresponding posterior distribution as shown in (Table 1) of the  $\lambda_{i,j,k}$  (i=1, 2 for test and control groups; j=1, 2, 3 for E/HR, IR, LR; k=1, 2, 3 for the three time intervals): Table 1. Lambdas by Risk Group, Time Interval, and Treatment

Risk Strata/Time Intervals	Patients completed 30 days [0-30] days	Patients completed 180 days [31-180] days	Patients completed 365 days [181-365] days
	Es	timated Lambdas (Test	Group)
Extreme or high risk (E/HR)	$\lambda_{1,1,1}$	$\lambda_{1,1,2}$	$\lambda_{1,1,3}$
Intermediate risk (IR)	λ 1,2,1	λ 1,2,2	λ 1,2,3
Low risk (LR)	$\lambda_{1,3,1}$	$\lambda_{1,3,2}$	$\lambda_{1,3,3}$
	Estimated Lambdas (Control Group)		
Extreme or high risk (E/HR)	λ 2,1,1	λ 2,1,2	$\lambda_{2,1,3}$
Intermediate risk (IR)	$\lambda_{2,2,1}$	λ 2,2,2	$\lambda_{2,2,3}$
Low risk (LR)	$\lambda_{2,3,1}$	λ 2,3,2	$\lambda_{2,3,3}$

#### 3.1.5.4 Bayesian method for the hypothesis test

For each Bayesian piecewise exponential model, 10000 posterior samples for each  $\lambda_{i,j,k}$  are generated, the estimated 1-year primary endpoint event rates (PE\_ACURATE and PE\_Control) for each sample of  $\lambda_{i,j,k}$  can be calculated based on the following:

Form/Template 90702621 Rev/Ver AF ACURATE IDE SAP 92400558, Rev/Ver I Page 28 of 64

$$\begin{aligned} &\text{PE}_{\text{ACURATE, E/HR}} = 1 - e^{-(31*\lambda_{1,1,1} + 150*\lambda_{1,1,2} + 185*\lambda_{1,1,3})}, \\ &\text{PE}_{\text{Control, E/HR}} = 1 - e^{-(31*\lambda_{2,1,1} + 150*\lambda_{2,1,2} + 185*\lambda_{2,1,3})}, \\ &\text{PE}_{\text{ACURATE, IR}} = 1 - e^{-(31*\lambda_{1,2,1} + 150*\lambda_{1,2,2} + 185*\lambda_{1,2,3})}, \\ &\text{PE}_{\text{Control, IR}} = 1 - e^{-(31*\lambda_{2,2,1} + 150*\lambda_{2,2,2} + 185*\lambda_{2,2,3})}, \\ &\text{PE}_{\text{ACURATE, LR}} = 1 - e^{-(31*\lambda_{1,3,1} + 150*\lambda_{1,3,2} + 185*\lambda_{1,3,3})}, \\ &\text{PE}_{\text{Control, LR}} = 1 - e^{-(31*\lambda_{2,3,1} + 150*\lambda_{2,3,2} + 185*\lambda_{2,3,3})}, \end{aligned}$$

The overall weighted 1-year primary endpoint rates for each sample from the posterior distributions are calculated as the following:

 $PE_{ACURATE} = 35\%* PE_{ACURATE, E/HR} + 30\%* PE_{ACURATE, IR} + 35\%* PE_{ACURATE, LR} PE_{Control} = 35\%* PE_{Control, E/HR} + 30\%* PE_{Control, IR} + 35\%* PE_{Control, LR}$ The treatment difference (PE\_ACURATE minus PE\_Control) will be calculated. Iterating this sampling process for 10000 times over the posterior distributions of the lambdas, the posterior distributions of the primary endpoint rate by treatment group and the posterior distribution of the treatment difference can be constructed for the hypothesis test on the primary endpoint. Similarly, the credible intervals will be constructed based on these posterior distributions. The non-inforiority test then is performed based on the prespecified success criteria: the posterior probability of H1 given the observed interim data is greater than the threshold  $\xi$ . If the posterior probability is greater than the pre-specified threshold  $\xi$ , then the non-inferiority is declared. To be specific, if the posterior probability of the treatment difference (PE\_ACURATE minus PE\_Control) <  $\Delta$  constructed from the sampling distribution (N=10000) is greater than the pre-specified threshold  $\xi$ , then the non-inferiority is declared.

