# 5 ADDITIONAL DATA ANALYSES

# 5.1 Adjudicated CEC Event Analysis

For clinical events, the cut-off for events for 30-day endpoints will be 30 days, for 6month endpoints it will be 180 days, for 1-year endpoints it will be 365 days, and for endpoints at 2–10 years it will be 365 days times the number of years. For events at discharge or 7 days post-procedure, the cut-off for events will be the earlier date of discharge or 7 days post-procedure for each subject. The number of evaluable subjects for the CEC event includes subjects who have CEC confirmed events or are in study at least 23, 150, or 335 days (defined as sufficient follow-up in Section 7.3.3) for 30-day, 6month, or 1-year outcome analysis, respectively. For analysis at 2-10 years, the sufficient follow-up is defined as "number of years times 365 minus 45". The number of evaluable subjects for the CEC event at discharge will include all subjects in the specific analysis set.

The Kaplan-Meier rates for all CEC Events will be provided in analyses at 30 days, 6month, and 1-10 years. The survival analysis (including accumulated event curve) for time-to-event endpoint will be provided for selected CEC events, and log-rank test pvalue and wilcoxon test p-value will be provided for comparing two survival curves.

Event to be analysed include the following:

- o Mortality: all-cause, cardiovascular, and non-cardiovascular
- Stroke: disabling and non-disabling
- Myocardial infarction (MI): periprocedural (≤72 hours post index procedure) and spontaneous (>72 hours post index procedure)
- Bleeding: life-threatening (or disabling) and major (through 5 years)
- Acute kidney injury (AKI; ≤7 days post index procedure): based on the AKIN System Stage 3 (including renal replacement therapy) or Stage 2
- Major vascular complications (through 5 years)
- Repeat procedure for valve-related dysfunction (surgical or interventional therapy)
- Hospitalization for valve-related symptoms or worsening congestive heart failure (NYHA class III or IV)
- New permanent pacemaker implantation resulting from new or worsened conduction disturbances
- New onset of atrial fibrillation or atrial flutter
- Coronary obstruction: periprocedural (≤72 hours post index procedure)
- Ventricular septal perforation: periprocedural ( $\leq$ 72 hours post index procedure)
- Mitral apparatus damage: periprocedural ( $\leq$ 72 hours post index procedure)
- Cardiac tamponade: periprocedural (≤72 hours post index procedure)
- Valve migration

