#### 7.3.2 Days to Last Follow-up

Valid Data Sources

- Adverse Event Form
- Hospitalization Form
- Procedure Form
- Date of Visit Form
- CEC data
- End of Study

Valid Data Points

- Adverse event dates are "Onset date", "If Hospitalization, is this a new hospitalization, If Yes, admission date", and "If Yes, discharge date" from the Adverse Event Form.
- Admission and Discharge dates are "Admission date" and "Discharge date" from the Hospitalization Form.
- Procedure date is "Date of Procedure" from the Procedure Form.
- Enrollment date is "Date of Enrollment" from the Screening and Additional Informed Consent Form
- Follow-up visit date is "Date of Visit" from the Date of Visit Form at each of the visits (discharge or 7 days post-procedure, 30 days, 6 months, and 1 to 10 years post-procedure).
- CEC event date date of event as adjudicated by the CEC
- End of Study dates of subject withdrawal consent and death.

Last follow-up date will be the latest of the following dates for each subject:

adverse event onset date, admission and discharge dates from hospitalization, procedure date, enrollment date discharge or follow-up visit date, and CEC event date.

If a subject died or withdrawn consent, the date of death or withdrawal (which even came first) should be the last follow-up date.

Follow-up days will be calculated for intent-to-treat analysis set and implanted analysis set

Day 0 is randomization date (ITT) or the procedure date (Implanted)

Days to last follow-up = last follow-up date – randomization date (ITT)/procedure date (Implanted).

Days to (event or last known status) = (event or status) date - randomization date (ITT)/procedure date (Implanted).

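### The 1-year rate formulas in SAP 3.1.5.4 add up to 366 days, while the SAP's own model and likelihood run to 365

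*SAP*

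**What the plan says.** SAP 3.1.4.1 sets the partition as "0 = t_0 < t_1 < t_2 < t_3 = 365$ , where $t_1 = 30$ and $t_2 = 180". In the last branch of its event probability, "1 - e^{-(\lambda_{j,1}*(t_{1}-t_{0})+\lambda_{j,2}*(t_{2}-t_{1})+\lambda_{j,3}*(\tilde{t}-t_{2", the first hazard is multiplied by t1 − t0, which is 30.

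SAP 3.1.4.3 defines exposure in the likelihood. A subject who passes the end of an interval contributes "t_{k} - t_{k-1}, if \ \tilde{t}_{m} \geq t_{k", so at most 30 days in interval 1.

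SAP 7.3.2 states "Day 0 is randomization date (ITT) or the procedure date (Implanted" and calculates days as one date minus another. SAP 5.1 sets the event cut-off: "for 1-year endpoints it will be 365 days".

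SAP 3.1.5.4 then computes the 1-year rates for three risk strata in two arms. The first formula begins "1 - e^{-(31*\lambda_{1,1,1} + 150*\lambda_{1,1,2} + 185*\lambda_{1,1,3", and the other five use the same 31, 150 and 185. SAP 3.1.6 carries the same model to the final analysis.

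**The concern.** A day multiplier has to be on the time scale on which its hazard was estimated. Here the first-interval hazard is events divided by exposure of at most 30 days per subject, and it is then applied over 31 days. The second and third multipliers match the model; only the first does not.

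These formulas produce both arms' posterior rates, their credible intervals and the posterior probability compared with the 97.5% threshold. A programmer working from 3.1.4.1 and one working from 3.1.5.4 would report different primary results. The SAP does not say which width lies behind its operating characteristics.

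**Working it through.** **Interval widths.** From the cut points in 3.1.4.1: 30 − 0 = 30, 180 − 30 = 150, 365 − 180 = 185, total 365. The figure in 3.1.5.4 is 31 + 150 + 185 = 366. The SAP's 31 is reproduced only by counting the integer labels 0 to 30 inclusively; the labels 31–180 and 181–365 give 150 and 185.

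**Effect on the arm rates.** Inputs are the control rate of 22.3% and test rate of 30.3% (SAP 3.1.9.1) and the hazard ratios r2 = λ2/λ1 and r3 = λ3/λ1 (SAP Table 3). Set λ1 so that the 365-day rate equals the planned rate p:

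λ1 = −ln(1 − p) / D, with D = 30 + 150×r2 + 185×r3.

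One further day at λ1 gives: rate with 31 = 1 − (1 − p)×exp(−λ1).

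For Case 2, D = 30 + 45 + 37 = 112.
- Control: λ1 = 0.2523/112 = 0.00225, and 1 − 0.777×exp(−0.00225) = 22.47%.
- Test: λ1 = 0.3610/112 = 0.00322, and 1 − 0.697×exp(−0.00322) = 30.52%.

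| Case (r2, r3) | D | 22.3% becomes | 30.3% becomes | Difference (true 8.00) |
|---|---|---|---|---|
| 1 (0.4, 0.3) | 145.5 | 22.43% | 30.47% | 8.04 |
| 2 (0.3, 0.2) | 112 | 22.47% | 30.52% | 8.05 |
| 3 (0.3, 0.1) | 93.5 | 22.51% | 30.57% | 8.06 |
| 4 (0.2, 0.2) | 97 | 22.50% | 30.56% | 8.06 |

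With the steepest historical ratios in SAP Table 4 (0.11 and 0.08), the arms rise by 0.32 and 0.41 points and the difference becomes 8.09.

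**Direction of the difference.** It does not move when the arms are equal. It moves slightly away from zero when both arms share a hazard pattern, which is slightly conservative if the test arm is worse. Pairing each test case with each control case (16 combinations) gives 7.96 (test Case 1, control Case 3) to 8.13 (test Case 3, control Case 1). The difference shrinks in 3 of the 16, all with the test arm on Case 1.

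**Effect on the posterior probability.** The closed-form Gamma(0.0001 + events, 0.0001 + exposure) posteriors were used with weights 35/30/35%, expected event counts and 2,000,000 draws. The control rate was 22.3%, and the test rate was solved so that the 30-day formula gives Pr(H1|Data) of about 97.5%. Assumptions: the same rate in every risk stratum (the SAP gives none), the same hazard case in both arms, SAP Table 2 counts at the interim, and 262/225/262 per arm without attrition at the final. Replacing 30 by 31 lowers Pr(H1|Data) as follows:

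| | Case 1 | Case 2 | Case 3 | Case 4 |
|---|---|---|---|---|
| Interim (points) | 0.07 | 0.10 | 0.13 | 0.11 |
| Final (points) | 0.10 | 0.13 | 0.16 | 0.15 |

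For comparison, the Monte Carlo standard error from 10,000 independent draws is sqrt(0.975×0.025/10000) = 0.16 points.

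**Effect on the test.** This was checked with 2,000 simulated trials of 3,000 posterior draws each, Case 2 hazards, Table 2 counts and threshold 97.5%:

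| Stratum rates | Interim power, 30 → 31 | Interim type I error, 30 → 31 |
|---|---|---|
| Equal | 92.25% → 92.05% | 2.85% → 2.65% |
| Control 35/20/11.6% (assumed); test 8 points higher for type I error | 94.70% → 94.65% | 2.45% → 2.30% |

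The interim decision changed in 1 to 6 of the 2,000 trials.

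**The case against.** The SAP also uses an inclusive day grid. SAP 3.1.9.1 defines the hazard on days 0–30, 31–180 and 181–365, and these labels recur in other sections. Days 0 to 365 are 366 calendar dates, so the Day 0 rule and the 365-day cut-off could be read to fit 31. On that view 3.1.5.4 follows one of two conventions, and the choice between them is open. The program is not in the documents; if it credits 31 days of exposure, the rates are not biased. The shifts in posterior probability are no larger than the Monte Carlo error, and both the 16 pairings and the equal stratum rates are reviewer assumptions.

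Part of this stands. The inclusive grid is the likely origin of the 31, the effect on the decision is negligible, and the posterior shifts are illustrative. It does not rescue the formula. Follow-up time is a plain difference of dates, so a subject followed to day 365 contributes 365 days. The stated likelihood never credits a 31st day in interval 1. A count of calendar dates cannot multiply a hazard estimated per elapsed day.

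**Conclusion.** The concern holds: as written, the six formulas are inconsistent with the SAP's own model and likelihood. Each arm's 1-year rate is overstated, by about 0.14 to 0.27 points over the Table 3 cases at the planned rates. The overstatement largely cancels in the treatment difference, and the residual can go either way if the arms have different hazard patterns. Type I error and power are not materially changed.

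The overstatement assumes that the program credits exposure as 3.1.4.3 states. The size of the posterior shift rests on the stratum-rate and follow-up assumptions given with the calculation. The mismatch itself rests on no assumption. It is worth correcting because this is a pre-specified primary-analysis formula, not because the conclusion is at risk.

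**What to change.** Replace 31 with 30 in all six formulas of SAP 3.1.5.4, so that they match 3.1.4.1 and 3.1.4.3 and sum to 365. If day 0 is meant to count as a full day, keep 31, and add that day to the first-interval exposure in 3.1.4.3 and to the probability formula in 3.1.4.1.

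In either case, state which width was used in the simulations behind Table 5 and the two tables numbered 6. The cost of the first option is one number in six formulas, the matching line of code and one sentence; the second also changes the exposure definition. The simulations need re-running only if their width differs from the corrected formula.
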